5.5.4. Cardiopulmonary Exercise Testing (CPET)

Symptom-limited cardiopulmonary exercise testing using a bicycle ergometer will be performed on Day 2 and Day 29. At baseline and during the exercise period the collected data will include but is not limited to: SpO₂ and arterial blood gases, VO₂ max, ventilation and lactate thresholds. Guidelines developed by ATS and American College of Chest Physicians will be used for conducting the test and interpreting the results ([ATS 2003](#)).

Instructions for the conduct of the CPET will be provided in a separate manual. An arterial line placement will be part of the CPET procedure. If the subject refuses arterial line placement they may still undergo the CPET assessments without the arterial line.

Agreement to undergo the CPET is not required for entry into the study; but participation is strongly encouraged.

5.5.5. Patient Reported Outcome (PRO) Measures

PRO assessments should be self-administered by the subject, using the paper questionnaires provided by the Sponsor, at the investigational site prior to all other non-PRO assessments (except in cases when the screening 6MWT is being repeated on Day 1 prior to any Day 1 visit assessments) and before the patient receives any disease-status information during that assessment. They will be administered as indicated in the schedule of assessments ([Appendix A](#)).

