5.5.2. Oxygen Saturation

During screening and with all scheduled vital sign assessments resting, room air oxygen saturation (SpO₂) will be measured by pulse oximetry (provided by the Sponsor) whilst the subject is seated and resting for at least 5 minutes. Before recording the SpO₂ value in the eCRF the study staff should ensure the measurement is stable, which may require continuous or repeated measurements and ensuring the subject is resting.

SpO₂ will be also be collected at baseline, during and following completion of the 6MWT and cardio-pulmonary exercise testing.

5.5.3. 6-Minute Walk Test (6MWT)

Functional exercise capacity will be evaluated at Baseline and Days 15, 28 and 58 using the 6-minute walk test. The 6MWT will be performed without the subject using supplementary oxygen. Oxygen may be used at any time during the 6MWT, if in the opinion of the Investigator or testing technician it is required for safety reasons. The 6MWT should then be stopped.

The baseline 6MWT performed at screening must be performed within 7 days of the Day 1 visit. If the 6MWT falls outside of the 7-day window, it must be repeated (the repeat may occur at the time of the Day 1 visit prior to any Day 1 visit assessments).

Guidelines developed by the ERS/ATS will be used for conducting the test and interpreting the results ([ATS 2002](#) and [Holland 2014](#)). Instructions for the conduct of the 6MWT will be provided in a separate manual.

The 6MWT should be performed at each scheduled visit at approximately the same time of day (e.g. in the morning) and after spirometry and DL_{CO} assessments (if scheduled on the same Visit day).

As part of the 6MWT, SpO₂, heart rate and the Borg dyspnea scale will be measured at the following time points: prior to starting the test, during the test, at completion of the test, 1 minute and 2 minutes after test completion.

For safety reasons, all patients should be clinically stable prior to performing the 6MWT.

Absolute contraindications to the 6MWT include unstable angina or myocardial infarction during the previous month.

Relative contraindications to participation in the 6MWT include:

- Resting heart rate >120 or <60 beats per minute
- Systolic blood pressure >180 mmHg
- Diastolic blood pressure >100 mmHg

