Note: All assessments should be performed within the number of days (Window) as indicated for each scheduled visit day. All assessments should be performed prior to receiving study drug during the treatment period unless otherwise indicated. SGRQ, ATAQ, UCSD, Cough VAS should be performed before all other non-PRO assessments, followed by 12-lead ECG and then vital sign assessments.

CONFIDENTIAL

- a All screening evaluations must be completed and reviewed prior to Day 1 (Visit 2) to confirm the subject meets all eligibility criteria prior to randomization to the treatment period. In cases when the screening 6MWT is done more than 7 days prior to Visit 2, it must be repeated, up and through Day 1, prior to any Day 1 assessments.
- b All subjects who discontinue study or study drug prior to study completion and who are unwilling or unable to complete the remaining scheduled visits should return to the study site to complete all Day 45 (Visit 8) assessments (refer to [Section 6](#))
- c Written informed consent must be obtained and documented prior to performing any study-specific screening procedure
- d Demographics, medical history and baseline conditions obtained at screening should be reviewed again at this visit and any changes since screening updated in the eCRF
- e Includes evaluation of the head, eyes, ears, nose and throat and cardiovascular, respiratory, musculoskeletal, gastrointestinal, neurological, dermatologic systems. No rectal or pelvic examination is required. Record any observed abnormalities in the eCRF. At subsequent visits record new or worsened clinically significant findings on the eCRF
- f Perform a limited, symptom-directed examination as clinically indicated. Record new or worsened clinically significant findings in the eCRF.
- g Includes heart rate, respiratory rate, systolic and diastolic blood pressure and temperature measured whilst in a semi-recumbent or supine position and resting for at least 5 minutes.
- h Performed while the subject is seated and resting for at least 5 minutes.
- i Perform 12-lead ECG in triplicate; three separate tracings with approximately 1 minute between each tracing, after resting in a semi-recumbent or supine position for at least 5 minutes.
- j After informed consent but prior to randomization only serious adverse events (SAEs) resulting from a protocol-mandated intervention should be reported. After randomization, all adverse events will be reported until study completion (Day 58).

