- k Performed for all female patients who are not post-menopausal or surgically sterile
- l If a urine pregnancy test is positive the result must be confirmed with a serum pregnancy test
- m PK blood samples during the treatment period should be collected on Days 1 and 28: Pre-dose and 2 hours post dose (+/- 15 minutes); Day 2: 24 hours (+/-2 hours) after the Day 1 dose *and* prior to receiving the Day 2 dose; Days 8 and 15: Pre-dose only.
- n Instructions for per-protocol performance of the 6-minute walk (and Borg dyspnea scale) and cardio-pulmonary exercise tests are provided in the procedure manual. Note: The baseline 6MWT performed during screening must be performed within 7 days of the Day 1 visit.
- o An unblinded study pharmacist will prepare daily doses of study drug, dispensed into 30 mL high-density polyethylene (HDPE) bottles. Each bottle (or dose) is packaged individually with 3 capsules of active or placebo or both specific to each subject's assigned treatment group. Subjects who have their dose modified during the study must return to the site to have the modified dose of study drug dispensed by the unblinded pharmacist.
- p Subjects should not administer study drug on the morning of these study visits. Study drug will be administered by the study staff after completion of all pre-dose assessments.
- q The SGRQ, ATAQ and UCSD questionnaires and cough VAS should be self-administered by the subject, using the paper forms provided by the Sponsor prior to all other non-PRO assessments and before the patient receives any disease-status information during that assessment. ATAQ questionnaires should be administered to subjects enrolled in Part B of the study.
- r The End of Study Questionnaire should be administered to subjects enrolled in Part B of the study.

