10.2 Definition of Baseline

For all endpoints, baseline is defined as the last non-missing measure or the average of the non-missing measures before the first dose of study drug. Change from baseline to follow-up visit will be calculated as the baseline measurement subtracted from the follow-up measurement for all assessments with the exception of the CPET endpoints. The first measurements for CPET endpoints occur at Study Day 2. The change from Day 2 to Day 29 will be calculated as the Day-2 measurement subtracted from the Day-29 measurement for all CPET endpoints.

The percent change from baseline values to post-baseline values will be calculated using the following formula where applicable:

$$([\text{post-baseline value} - \text{baseline value}] / \text{baseline value}) \times 100\%$$

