17.3 UCSD Shortness of Breath Questionnaire

The UCSD Shortness of Breath Questionnaire is completed at Baseline (Day 1), Day 8, Day 15, Day 28, Day 45, and Day 58. The questionnaire is comprised of 24 questions each scored on a scale of 0 to 5. Total score ranges from 0 to 120 where higher scores indicate worse severity due to shortness of breath. Scores for each question answered will be summed to provide a total score. Missing responses are not included in the calculation of the total score.

Summary statistics for the UCSD Shortness of Breath Questionnaire total score will be displayed by study drug and all GBT440, and by visit for the Efficacy-Evaluable population using actual data collected at the site. The change and percent change from baseline to each post-baseline visit also will be summarized and displayed.

ANCOVA models will be used to analyze the effect of treatment on the change from baseline with baseline value as a covariate. Least squares (LS) means and SEs will be displayed for the change from baseline in each treatment group and for all GBT440.

LS means (95% CI) and p-values from the models will be used to make the following comparisons:

- GBT440 600 mg – Placebo
- GBT440-900 mg – Placebo
- GBT440-1500 mg – Placebo
- All GBT 440 – Placebo

Total scores will be provided in a subject listing of UCSD Shortness of Breath Questionnaire results.

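### When the baseline 6MWT is repeated on Day 1, the only pre-dose SGRQ, UCSD, cough VAS and ATAQ may be completed after the walk, although later ones precede it or have no walk, and Appendix A carries no such exception (minor)

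*Protocol*

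**What the plan says.** Screening runs from Day -21 to Day -1. A screening 6MWT done more than 7 days before Day 1 does not stand; under Protocol Appendix A, note a, "it must be repeated, up and through Day 1, prior to any Day 1 assessments". Protocol 5.1 and 5.5.3 say the same, and SAP section 16 expects such cases, since it takes the baseline walk from screening or from a Day 1 repeat.

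Protocol 5.5.5 requires questionnaires before all non-PRO assessments, "except in cases when the screening 6MWT is being repeated on Day 1 prior to any Day 1 visit assessments". Appendix A has no such exception. Its general note says "SGRQ, ATAQ, UCSD, Cough VAS should be performed before all other non-PRO assessments", and note q says they are completed "prior to all other non-PRO assessments and before the patient receives any disease-status information during that assessment". Note q is repeated in SAP 5.1, as is the general note (there without ATAQ).

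No questionnaire is scheduled at screening. SAP 17.3 is typical: "The UCSD Shortness of Breath Questionnaire is completed at Baseline (Day 1), Day 8, Day 15, Day 28, Day 45, and Day 58". The two documents differ on which later visits include SGRQ, but in both Day 1 is its only pre-dose visit.

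On analysis, SAP 10.2 states that "baseline is defined as the last non-missing measure or the average of the non-missing measures before the first dose of study drug". SAP 17.3, like the other questionnaire sections, states that "ANCOVA models will be used to analyze the effect of treatment on the change from baseline with baseline value as a covariate". Neither document flags a questionnaire completed after a walk or plans a sensitivity analysis for it.

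**The concern.** A subject whose walk is repeated on Day 1 walks without supplemental oxygen, having been selected for falling below 88% SpO2 on that test, and then rates cough and breathlessness. No rest interval between the two is stated. At Days 15, 28 and 58 the same subject rates symptoms before walking; at Days 8 and 45 there is no walk. If the walk worsens the Day 1 rating, later scores look improved without any drug effect.

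This matters because change from baseline within each arm is itself a planned display: Protocol 2.3 frames the symptom objective as Day 28 against baseline, and the SAP reports least squares mean change by arm. The arms are also very small, so an uneven spread of affected subjects can move a treatment difference. Sites meanwhile have two conflicting instructions on the order of assessments at that visit.

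Exposure differs by instrument. Cough VAS, with no stated recall period, is the most plausible. UCSD (no stated recall, but about daily activities) and ATAQ Symptoms (24 hours) are possible. SGRQ (4 weeks) and ATAQ Impacts (1 week) are less so. The Borg scale is unaffected because it is taken within the walk at every 6MWT.

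**Working it through.** The plan gives no figure to reproduce. The order of assessments follows from the text; the size has to be expressed through two unknowns.

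**Order.** Day 1 with a repeat: walk, then questionnaires (5.5.3, note a, 5.5.5). Days 15, 28, 58: questionnaires, then walk (5.5.5, general note, note q). Days 8 and 45: questionnaires, no walk.

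**Inputs.** Planned arms (Protocol 3.1): Part A 6/6/6 (900 mg, 600 mg, placebo); Part B 9/3/3 (1500 mg, 600 mg, placebo). Pooling the common arms (Protocol 11, SAP 10.3) gives placebo 9, 600 mg 9, 900 mg 6, 1500 mg 9, all GBT440 24. ATAQ is Part B only. Let q be the share of subjects with a Day 1 repeat and d the mean post-walk worsening in points. The documents give neither.

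**Range for q.** Days -21 to -8 are 14 of 21 screening days, and 14/21 = 67%. That is an upper guide, reached only if walks are spread evenly over screening and every repeat is done on Day 1. Sites are told to walk within 7 days of Day 1, and repeats may be done earlier than Day 1, so q could be near 0.

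**Within-arm change.** The arm mean shifts towards improvement by q × d: 0.10d, 0.25d, 0.33d, 0.50d and 0.67d at q = 10%, 25%, 33%, 50% and 67%. Baseline adjustment does not remove a shift common to all arms.

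**Chance imbalance between arms.** SD = d × √[q(1−q)(1/n1 + 1/n2)], for unadjusted change:

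| q | 6 v 9 (900 mg v placebo) | 9 v 9 (600 or 1500 mg v placebo) | 24 v 9 (all GBT440 v placebo) | 9 v 3 (ATAQ, 1500 mg v placebo) |
|---|---|---|---|---|
| 10% | 0.16d | 0.14d | 0.12d | 0.20d |
| 25% | 0.23d | 0.20d | 0.17d | 0.29d |
| 33% | 0.25d | 0.22d | 0.18d | 0.31d |
| 50% | 0.26d | 0.24d | 0.20d | 0.33d |
| 67% | 0.25d | 0.22d | 0.18d | 0.31d |

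For example, at 33%: √(0.33 × 0.67 × 2/9) = 0.22 and √(0.33 × 0.67 × 4/9) = 0.31. ANCOVA multiplies these by the slope of follow-up on baseline. With an assumed slope of 0.7 and an assumed d of 10 points, they become about 1.6 points (9 v 9) and 2.2 points (9 v 3).

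**Pooling across Parts.** Let qA and qB be the shares in each Part. Pooled placebo has share (6qA + 3qB)/9; the 1500 mg arm has qB. The difference is qB − (2qA + qB)/3 = (2/3)(qB − qA). In unadjusted change, the 1500 mg contrast is therefore biased by (2/3)(qB − qA)d, towards benefit if qB is larger. Assumed shares of 20% in Part A and 50% in Part B give 0.2d. The stated ANCOVA has no term for Part; it would scale this bias by the slope rather than remove it. The pooled 600 mg arm has the same Part mix as placebo, so its contrast has no such bias. ATAQ, confined to Part B, is also free of it.

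**The case against.** The strongest reply is that the repeat walk precedes randomisation and dosing, so within a Part it cannot favour an arm in expectation. Every planned PRO test is against placebo, and chance imbalance is noise already carried in the confidence interval. With an assumed SD of change of 10 to 20 points, the 9 v 9 standard error is 4.7 to 9.4 points. Adding an SD of 2.2 points (q = 33%, d = 10) widens it by only about 3% to 11%. That stands. It does not cover the within-arm displays or the 1500 mg contrast against placebo pooled across Parts.

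The exception also looks deliberate: the repeat walk supports eligibility, and Protocol 5.1 wants screening finished before any Day 1 assessment. That explains the order but does not require it, because the walk can follow the questionnaires and still precede randomisation.

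A reader might make two stronger inferences.

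- **That the rule on disease-status information is broken.** The documents do not support this. The exception in 5.5.5 qualifies only the order relative to other assessments; the condition on disease-status information still applies on Day 1. Nothing says subjects are told their walk result first.
- **That a raised Day 1 heart rate would hide a later rise.** This is not shown. Vital signs follow at least 5 minutes' rest and are also taken at screening, and SAP 10.2 allows baseline to be an average of pre-dose values.

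**Conclusion.** The point holds as a minor one. For subjects whose walk is repeated on Day 1, the baseline SGRQ, UCSD, cough VAS and ATAQ can be post-walk while later scores are not. Neither document corrects this, and 5.5.5 conflicts with the general note and note q of Appendix A.

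The effect is a possible false within-arm improvement of q × d, plus added noise between arms. There is no expected between-arm bias within a Part; across Parts, the 1500 mg contrast is biased only if the repeat share differs. A reader might infer a demonstrated bias, or that two thirds of subjects are affected. The documents support neither: the repeat share, the shift and the slope are all assumptions, and a share near zero is possible. The endpoints are exploratory, with no formal hypotheses and no multiplicity control. The case for acting is the low cost and the conflicting instructions.

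**What to change.** Delete the exception in Protocol 5.5.5. State that on Day 1 the questionnaires are completed first, and that the repeat 6MWT is then done and evaluated before randomisation. This keeps the eligibility check and restores the order used at Days 15, 28 and 58. Amend Protocol 5.1 (both the repeat-walk sentence and the one requiring screening to be complete before Day 1 assessments), 5.5.3, Appendix A note a and SAP 5.1 note a to match. The general note and note q can then stand.

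For subjects already enrolled, add a flag for a Day 1 repeat to the analysis data, report its frequency by arm and Part, and show the PRO summaries without flagged subjects as a sensitivity table.

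The cost is a handful of sentences across the two documents, one flag and one table. Some questionnaires will be wasted when a subject fails the repeat walk. The table will be imprecise: at a 33% share, the 9 v 3 ATAQ comparison falls to about 6 v 2.

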5.5.5.1. St George's Respiratory Questionnaire (SGRQ)

The SGRQ is a symptom-specific 2-part, patient self-administered questionnaire that assesses shortness of breath while doing a variety of activities of daily living. This questionnaire comprises three domains: symptoms, activity and impact. Items are assessed on various response scales, including a 5-point Likert scale and True/False scale. The SGRQ has a recall specification of 4 weeks. Paper questionnaires will be provided to sites prior to subject enrollment.

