2.3. Exploratory Objectives

- To evaluate the effect of GBT440 on distance walked during the 6MWT at Days 15 and 28 compared to baseline.
- To evaluate the effect of GBT440 on IPF-related symptoms using patient reported outcomes (PROs) at Day 28 compared to baseline.
- To evaluate the effect of GBT440 on cardiopulmonary exercise testing parameters at Day 29 compared to baseline.
- To evaluate pulmonary function, including assessment of spirometry and Diffusing Capacity of the Lung for Carbon Monoxide (DLco) at Day 28 compared to baseline.
- To evaluate the PK-PD relationship of GBT440 at Days 15 and 28 compared to baseline.

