8. DOSAGE AND TREATMENT ADMINISTRATION

8.1. Treatment Regimen

GBT440 and placebo will be administered orally each day for 28 days. GBT440 will be administered as 300 mg capsules. Placebo will be provided as capsules matching the GBT440 capsules. Subjects randomized to the following treatment groups will receive:

Part A:

- GBT440 900 mg: 3 GBT440 300 mg capsules.
- GBT440 600 mg: 2 GBT440 300 mg capsules and 1 placebo capsule.
- Placebo: 3 placebo capsules.

Part B:

- GBT440 1500 mg: 5 GBT440 300 mg capsules
- GBT440 600 mg: 2 GBT440 300 mg capsules and 3 placebo capsule.
- Placebo: 5 placebo capsules.

Instructions for Administration of Study Drug:

- Self-administered by subject in the morning
 - except on study visit days when the subject must not take study drug. It will be administered at the site after completion of scheduled assessments.
- May be taken with or without food
- May be taken with water or other non-alcoholic beverage

Subjects must be instructed not to take study drug the day of their scheduled visits (refer to [Appendix A](#)). Study drug will be administered at the site on these days, after completion of all the assessments scheduled for that visit.

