17.2 Saint George's Respiratory Questionnaire

The Saint George's Respiratory Questionnaire (SGRQ) is completed at baseline (Day 1), Day 8, Day 15, Day 28, Day 45, and Day 58. The SGRQ is a component-based questionnaire with 3 component scores (Symptoms, Activity, and Impacts) and a total score for all components. The method of calculating all component scores and total score is detailed in the SGRQ manual provided in the Appendix to this SAP.

The questions and response weights used in the scoring algorithm are presented in Section 7 of the SGRQ manual. The responses to Questions 1-8 are used to calculate the Symptoms component score. The Symptoms questions are designed to assess subjects' perception of their respiratory problems over the preceding 3 months. The Activity component score is calculated from the responses to Questions 11 and 15, which measure disturbances to subjects' daily physical activity. The Impacts component score is calculated from the responses to Questions 9-10, 12-14, and 16-17. The Impacts component score assesses disturbances of psycho-social function resulting from subjects' respiratory problems. Subjects who are not receiving respiratory treatment are scored weight values corresponding to a

response of “False” for Question 14. A Total score that summarizes the impact of the disease on overall health status also is calculated. Each component score and the total score are expressed as a percentage of overall impairment where 100 represents the worst possible health status and 0 indicates the best possible health status. No imputation for missing values will be performed. The scoring algorithms account for unanswered questions.

Summary statistics for each component score and total score will be displayed by study drug and all GBT440, and by visit for the Efficacy-Evaluable population. The change from baseline to each post-baseline visit also will be summarized. Self-described current health status (very poor, poor, fair, good, or very good) at each visit will be summarized with the number and percent of subjects in each category. Additionally, subjects receiving respiratory treatment and those who reported other activities stopped by respiratory problems at each visit will be summarized with the number and percent of subjects by study drug and overall.

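### The protocol gives the SGRQ a 4-week recall, the SAP gives its Symptoms questions 3 months; on a 3-month form only about 30% of the Day 28 Symptoms window is on treatment

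*Protocol*

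**What the plan says.** **Recall period.** Protocol 5.5.5.1 gives one figure for the instrument, with no exception by domain: "The SGRQ has a recall specification of 4 weeks". SAP 17.2 says that the Symptoms questions capture the subject's "perception of their respiratory problems over the preceding 3 months" and identifies those items: "The responses to Questions 1-8 are used to calculate the Symptoms component score". It gives no recall period for Activity or Impacts. Section 19 of the SAP, which lists departures from the protocol, is silent on SGRQ recall.

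**Treatment and timing.** Protocol 8.1: "GBT440 and placebo will be administered orally each day for 28 days". Appendix A adds: "All assessments should be performed prior to receiving study drug during the treatment period unless otherwise indicated". The Day 28 visit has a window of 2 days either side.

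**Visits.** Protocol Appendix A schedules the SGRQ on Days 1, 28 and 58. SAP 5.1 and 17.2 add Days 8, 15 and 45. The protocol is also not uniform within itself: the objective in 2.3 assesses symptoms "using patient reported outcomes (PROs) at Day 28 compared to baseline", while the endpoint in 3.2.3 names Days 15 and 28.

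**Use of the score.** SAP 17.2 analyses change from baseline by ANCOVA with the baseline value as covariate, and reports 95% confidence intervals and p-values for four comparisons with placebo. Scoring follows a manual appended to the SAP. Protocol section 11 and SAP 10.3 pool the 600 mg and placebo arms across Parts A and B.

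**The concern.** One of the two statements misdescribes the questionnaire that subjects fill in. If sites hold a 4-week form, the SAP describes the Symptoms items wrongly, and someone has to check that the scoring manual fits the form. If sites hold a 3-month form, the protocol is wrong, and most of the period a subject is asked about at Day 28 lies before the first dose.

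In the second case the same pre-treatment weeks are recalled at baseline and again at Day 28. The Symptoms change score then largely compares a period with itself, and a small or absent difference from placebo says little about 28 days of treatment. Symptoms also feeds the Total score, so part of the problem carries over. The recall period changes the meaning of the follow-up visit as well: whether Day 58 measures time off treatment depends on which window applies.

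**Working it through.** The documents give no figure for the overlap between recall window and treatment, so there is nothing to reproduce first.

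**Inputs**
- First dose on Day 1, daily dosing for 28 days (Protocol 8.1).
- Assessments precede the day's dose (Protocol Appendix A), so 27 days of treatment have elapsed at a nominal Day 28 visit, or 28 if Day 28 is counted.
- Recall window: 28 days (Protocol 5.5.5.1), or 3 months (SAP 17.2, Symptoms only). *Assumption:* 3 months is 90 to 92 days; the SAP does not give it in days.

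**Formula.** On-treatment share = treatment days inside the recall window / length of the window.

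| Visit | 3-month window | 4-week window |
|---|---|---|
| Day 8 | 7/92 = 7.6% to 8/90 = 8.9% | 7/28 = 25.0% to 8/28 = 28.6% |
| Day 15 | 14/92 = 15.2% to 15/90 = 16.7% | 14/28 = 50.0% to 15/28 = 53.6% |
| Day 28 | 27/92 = 29.3% to 28/90 = 31.1% | 27/28 = 96.4% to 28/28 = 100% |
| Day 45 | 28/92 = 30.4% to 28/90 = 31.1% | 12/28 = 42.9% (Days 17–28) |
| Day 58 | 28/92 = 30.4% to 28/90 = 31.1% | 0/28 = 0% (window is Days 30–57) |

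**Visit window at Day 28, 3-month form.** Seen on Day 26: 25/92 = 27.2%. Seen on Day 30, with dosing continued to the visit: 30/90 = 33.3%. The range is therefore about 27–33%. A 4-week form on Day 26 gives at least 25/28 = 89.3%.

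**Overlap with baseline.** With a 91-day window at Day 28, 91 − 27 = 64 recalled days precede the first dose, or 64/91 = 70.3% (63/90 = 70.0% to 65/92 = 70.7%). All of them also fall inside the window recalled at the Day 1 baseline.

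**From overlap to attenuation.** If a subject's answer weights every recalled day equally, and the effect is constant from the first dose, the expected Symptoms effect at Day 28 is the true effect times the on-treatment share. The loss is 1 − 0.311 = 69% to 1 − 0.293 = 71%, or about 70%. If recent days carry more weight, the loss is smaller. The documents give no basis for choosing the weighting.

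**Follow-up contrast.** Under 4 weeks the treated share falls from 96–100% at Day 28 to 0% at Day 58. Under 3 months it is about 30% at both visits, so the contrast between treatment and follow-up disappears from the Symptoms score.

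**The case against.** The strongest reply is that the SAP sentence may be a general description of the instrument, carried over from a manual, and that sites held a 4-week form throughout. That is possible. Neither the form nor the manual is reproduced in the text, so the documents cannot rule it out. The contradiction stands all the same, because the SAP is the text that governs scoring and it does not declare the difference. SAP section 1 says that its statistical methods supersede the protocol's, but that settles the analysis, not which form subjects completed.

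Four stronger readings are tempting, and the documents do not support them:

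- *That the whole SGRQ is compromised, or that a null SGRQ result could not be interpreted.* The SAP ties 3 months to Questions 1–8 only. Activity and Impacts draw on Questions 9–17 and have no such statement. The weight of Symptoms within Total is not in the text, so the effect on Total cannot be quantified.
- *That a 70% loss of effect is established.* Only the 30% overlap is arithmetic. The 70% needs equal weighting of days. Even then the effect is reduced, not removed.
- *That the scores will be computed with the wrong algorithm.* Neither document says that the two recall versions are scored differently. This is something to check, not a demonstrated error.
- *That the answer is simply to declare the 4-week form.* Part A was already running: Protocol 1.5.3 refers to 12 subjects followed for up to 28 days and 16 who had completed 15 days. Changing forms for Part B could mix instruments within the pooled arms.

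It is also fair to say that little rests on this score. It is one of several exploratory patient-reported outcomes in a study with no formal hypotheses (SAP 3.4) and no statistically based sample size (SAP section 7).

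**Conclusion.** The two documents contradict each other on the recall period of the SGRQ Symptoms questions, and the difference is undeclared. Which form was used cannot be determined from them.

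The consequence is conditional. On a 3-month form, about 29–31% of the Symptoms window at Day 28 is on treatment (27–33% across the visit window), against 96–100% at nominal Day 28 on a 4-week form. This rests on 3 months being 90–92 days and on uninterrupted dosing from Day 1. The Symptoms change, and its unquantified share of Total, would be attenuated: about 70% under equal weighting of days, less if subjects favour recent days. Activity and Impacts are not shown to be affected.

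The visit-day conflict matters under either form, since even a 4-week window is only about 25% on treatment at Day 8 and 50% at Day 15. No primary or secondary conclusion depends on the SGRQ, so the point is worth correcting but of modest severity.

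**What to change.** Before any SGRQ scoring:

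1. Check the paper forms held at sites, and record which version and recall period was administered in Part A and in Part B.
2. State that version and recall period in Protocol 5.5.5.1 and SAP 17.2, and confirm that the manual appended to the SAP is the one for that version.
3. If a 3-month form was used in either part, state in SAP 17.2 that Symptoms and Total at or before Day 28 will not be interpreted as on-treatment measures for that part. Rely on Activity and Impacts, once the form confirms their recall period. If the forms differ between parts, do not pool Symptoms or Total across them.
4. Reconcile the SGRQ visits between Protocol Appendix A (Days 1, 28, 58), the Day 15 endpoint in Protocol 3.2.3, and SAP 5.1 and 17.2 (which add Days 8, 15 and 45). If Days 8 and 15 are kept, note that they are only partly on treatment even with 4-week recall.

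The cost is a check of the forms and manual and short wording changes in both documents. No new data are needed. If a 3-month form was used, the sponsor also gives up an on-treatment reading of Symptoms and Total up to Day 28.
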